General anesthesia is a state of pharmacologically induced, temporary, and reversible coma consisting of three elements: hypnosis, analgesia, and muscle relaxation. These are achieved by administering two or more drugs to the patient, inducing an artificial sleep so deep that it allows any surgical procedure to be performed without feeling any pain, moving, or remembering anything. This means that any noxious stimulus is neither processed nor recognized by the brain while anesthesia is in progress. This technique is typically used for long-duration or very painful procedures (ISSalute, 2022).

Deep sedation is defined as a drug-induced depression of consciousness during which patients cannot be easily awakened but respond to repeated or painful stimulation. In this state, the ability to maintain independent ventilatory function may be compromised, often requiring assistance to maintain airway patency. Spontaneous ventilation may be inadequate, whereas cardiovascular function is usually maintained (2019). Sedation is a continuum and can progress or regress from one level to another, inevitably varying the risks and appropriate management to preserve patient safety. Monitoring vital parameters, always combined with careful clinical assessment, is therefore indispensable and adjustable as needed (SIAARTI-SIED, 2022).

Deep sedation may be the anesthetic technique of choice for short-duration, particularly painful day-surgery procedures where complete patient curarization is not strictly necessary. Various drugs in current clinical practice can ensure an adequate sedation plan for the procedure, which can be used alone or in combination and administered as a single dose or continuous infusion.

In addition to standard perioperative monitoring, monitoring the depth of anesthesia is highly recommended by international scientific literature, especially in cases where a protocol involving Propofol infusion in TIVA-TCI (Total IntraVenous Anesthesia - Target Controlled Infusion) is used (Klein AA, 2021). Conversely, there is currently no recommendation or guideline for nociception monitoring. Nociception is typically assessed using indirect methods such as heart rate and blood pressure variations. However, these indicators have been shown to be poor surrogates for nociception monitoring, as vital signs are influenced by a range of other health conditions (Coluzzi, 2019).

Various other methods have been used to establish the efficacy of analgesics during the intraoperative period, such as evaluating patient movement and sweating. However, these indirect parameters are largely imprecise because different anesthetic drugs reduce and/or abolish the autonomic nervous system's ability to respond to nociceptive stimuli to varying degrees (Kang, 2015). Nevertheless, maintaining the balance between nociception and analgesia (the "nociception-antinociception balance") is critical to avoid serious postoperative complications (Ghanty, 2019).

It should also be noted that the lack of accurate nociception monitoring during surgery can lead to inadequate analgesic doses. Opioid analgesics are widely used in common clinical anesthetic practice, and administering an insufficient dose could lead to abnormal recovery, delayed hospital discharge, and, in some cases, chronic postoperative pain. On the other hand, administering an excessive dose of opioids can cause nausea, vomiting, respiratory depression, increased hospital stay, and treatment costs (Won, 2016).

Recognizing the complexity of this process, a medical monitoring device has been developed: the PMD-200™ provides the nociception level index (NOL), an innovative technology developed by Medasense Biometrics Ltd. that allows objective measurement of patient nociception by analyzing multiple patient parameters. This device uses a non-invasive finger probe with four sensors (photoplethysmography amplitude, galvanic skin response, peripheral temperature, and accelerometry) that extract multiple pain-related physiological signals. Real-time data are analyzed by specific algorithms that identify the patient's pain pattern, displayed on a numerical scale from 0 to 100. Notably, a value of 25 indicates the threshold beyond which the nociceptive reaction is clinically significant.

The use of this tool has been extensively studied during general anesthesia, demonstrating that monitoring nociception response levels with the NOL Index can help reduce postoperative pain, patient stress hormone levels (ACTH and cortisol) (Meijer, 2020), and intraoperative opioid use, resulting in fewer hypotensive events and associated myocardial and renal damage (Meijer, 2019). Additionally, it has been shown that the combined use of the NOL Index and Bispectral Index during general anesthesia can provide accurate and complementary information to guide optimal administration of analgesic and hypnotic drugs (Meijer, 2020).

The rationale for this study lies in the context of relatively short surgical procedures (lasting between 30 and 90 minutes) requiring deep sedation anesthesia. The hypnotic efficacy of commonly used sedation protocols is widely studied and validated by international scientific literature. It is also important to consider that, in some cases, excessive administration of sedatives with insufficient analgesic coverage may occur, leading to seemingly acceptable postoperative results, while in reality, patients experience painful situations without remembering them. This can be particularly dangerous in fragile patients, where heightened adrenergic system activation leads to serious complications.

Therefore, we ask: "Are our sedation protocols, aside from their hypnotic effectiveness, equally effective at the analgesic level?"

Finally, an ethical question must also be highlighted, as proper pain management, in all its forms, is a duty the clinician must address.

Study Purpose

Evaluate the efficacy of the sedation protocol from a nociceptive perspective through continuous intraoperative nociception monitoring (NOL Index).

Primary Objective

The sedation protocol will be considered nociceptively ineffective if the percentage of time the NOL index exceeds the threshold of 25, relative to the observation time, is greater than 25%.

The NOL Index observation time is defined as the interval between reaching an adequate sedation level (Bispectral Index - BIS between 40 and 60) and the end of surgical stimulation.

Secondary Objectives

1. Time the NOL index exceeds the threshold of 25, expressed in minutes
2. Number of peaks with NOL index above 40
3. Evaluate any correlation between the primary objective and the NRS scale 15 minutes post-operation
4. Evaluate any correlation between the primary objective and the NRS scale 2 hours post-operation
5. Evaluate any correlation between the primary objective and the need for rescue analgesic doses

requested by the patient.

Study Design

Prospective observational clinical study, non-profit, non-pharmacological, utilizing the medical device PMD-200™ (Medasense Biometrics Ltd), in patients undergoing short-duration (less than 90 minutes) and particularly painful surgical procedures, with an indication for deep sedation anesthesia.

Materials and Methods

Eligibility Criteria

Inclusion Criteria

- ✓ Adult patients (>18 years old)
- ✓ ASA Physical Status I - II - III

Exclusion Criteria

- ✗ ASA Physical Status IV
- ✗ Pregnant or lactating patients
- ✗ Pre-existing cardiac arrhythmias
- ✗ Patients with neuromuscular diseases
- ✗ Patients with psychiatric syndromes under pharmacological treatment
- ✗ Patients with chronic continuous use of analgesics
- ✗ Patients with a history of drug abuse
- ✗ Allergy to one or more active ingredients used in the protocol
- ✗ Refusal of consent

Study Population

The study population consists of patients admitted to the "Ss. Trinità of Borgomanero" hospital between March 1, 2024, and August 31, 2024, who need to undergo surgical procedures lasting less than 90 minutes and particularly painful, with an indication for deep sedation anesthesia.

Study Flow-chart

Before enrollment, upon arrival in the operating room and after being properly positioned on the operating table, patients will undergo standard intraoperative monitoring with pulse oximetry (SpO₂), 3-channel electrocardiography (ECG), non-invasive blood pressure (NIBP), Bispectral Index (BIS) sensor, and a nociception sensor (NOL) will also be placed. Patients will be preoxygenated with a facial mask with FiO₂ at 100% for 3 minutes. The induction phase of deep sedation anesthesia will be conducted with a single bolus of Fentanyl 1mcg/kg and TIVA-TCI of Propofol with a target-controlled infusion (C_E) concentration of 4.0 mcg/mL. As soon as the sedation plan shows a Bispectral Index between 40 and 60, the observation of the NOL Index will begin. Subsequently, the laryngeal mask will be positioned, mechanical ventilation initiated, and the surgical procedure commenced. During this phase, maintenance of the anesthesia plan will be ensured by the infusion of Propofol in TIVA-TCI with a C_E to maintain the BIS between 40 and 60, and the administration of Paracetamol 1 g, Ketorolac 30 mg, Dexamethasone 4 mg. At the end of the surgical procedure, the observation of the NOL Index will be concluded. Upon awakening, patients will be transferred to the Post-Anesthesia Care Unit (PACU), where they will remain until stabilization of vital signs. At this point, 15 minutes post-operation, the pain intensity will be recorded using the NRS scale. Subsequently, patients will be discharged to the ward,

where, at 2 hours post-operation, they will be interviewed regarding the intensity of post-operative pain and if they require any rescue analgesic doses.

Any procedures not explicitly expressed in the protocol will be performed according to normal clinical practice.

Collection and Management of Clinical Data

Data collection and management are entrusted to the investigator and/or study staff. Data collection will be directly performed on a digital file (spreadsheets - [name] - Microsoft, Redmond, CA) without the use of paper forms. Data will be collected anonymously without identifying codes that allow tracing back to the patient's folder and therefore to the patient's identity. The correspondence list between demographic data and patient identification codes will be kept at the enrolling center, and only the study staff will have access to it. The collected data will include the following:

Anthropometric Data

- Gender
- Age
- Weight
- Height
- Body Mass Index - BMI
- ASA Physical Status

Clinical Data

- Surgical Procedure performed
- Heart Rate (HR)
- Non-invasive Blood Pressure (NIBP)
- Pulse Oximetry (SpO2)
- Bispectral Index (BIS)
- NOL Index
- NRS Pain Scale

Statistical Analysis

Continuous variables will be presented as mean and standard deviation or as median and interquartile range depending on the distribution. Normal distribution will be assessed using the Kolmogorov-Smirnov test. Any sub-analyses and comparisons between subgroups will be performed using Student's t-test for parametric data, while the Mann-Whitney test will be used for non-parametric data. Categorical variables will be presented as absolute number and percentage relative to the total sample size. Any sub-analyses and comparisons between subgroups will be performed using the chi-square test or Fisher's exact test depending on the subgroup sizes. In all cases, the null hypothesis will be rejected for values of $\alpha < 0.05$. The software used for data analysis and sample sizing is Medcalc v. 22.013 (MedCalc Software, Ostend, Belgium).

Sample Size Determination

Following the manufacturer's indications, a nociceptive response measured at NOL >25 is considered

positive. In the absence of similar studies and reference parameters, we have set, based on clinical experience, a mean $\leq 10\%$ of the observation interval, with NOL ≥ 25 , as not significant for the presence of a nociceptive stimulus (Null Hypothesis). We have also considered a mean $\geq 25\%$ of the observation interval, with NOL ≥ 25 , as significant for the presence of a nociceptive stimulus. By calculating the sample size for a single mean, setting the type I error α to 0.05, power β to 0.8, estimating a standard deviation of 30%, the sample size in the study is determined to be 34 subjects.

Approval from the Competent Authority

In accordance with current regulations, the principal investigator must obtain approval from the appropriate Competent Authority before commencing the clinical study. This study will be conducted in accordance with the rules of ICH/GCP (International Conference of Harmonization/Good Clinical Practice) and all applicable laws, including the Helsinki Declaration of June 1964, modified by the latest World Medical Association General Assembly, Seoul 2008. As this is a non-interventional study, there are no specific risks associated with participating in the study protocol. Participation does not entail direct benefits to the enrolled patient but will contribute to improving knowledge regarding nociceptive stimulation during deep sedation anesthesia for patients undergoing short-duration and particularly painful surgical procedures.

Ethics Committee Approval

The investigator must ensure that the protocol has been reviewed and approved by the local independent Ethics Committee before commencing the study. The Ethics Committee must also review and approve the informed consent (IC) form and all written information provided to the patient before enrollment in the study. If it is necessary to modify the protocol and/or the IC during the study, the investigator will be responsible for ensuring the review and approval of such documents as requested by the Ethics Committee. The content of such modifications will be implemented only after approval by the Ethics Committee. Until then, reference should be made to the previous version of the already approved document.

Informed Consent

The investigator or other designated personnel is responsible for informing individuals about all aspects and procedures of the study. The IC must comply with current regulatory procedures: Helsinki Declaration (WMA, 2013 latest version, §§ 25-32), Reg. (EU) 536/2014, Charter of Fundamental Rights of the European Union (Nice, 2000, art. 3). The investigator (and/or designated collaborator) and the subject being offered the study must sign the IC form before the patient initiates any procedures indicated in the study. The subject will receive a dated and signed copy of the IC from both parties, and the original copy will be kept in the designated archives for the study. The subject's decision to participate or not in the study must be entirely voluntary. The participating subject has the right to withdraw their consent at any time.

Confidentiality

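### The rule for calling the sedation protocol ineffective (more than 25% of time) is not the decision the 34 patients were sized for (rejecting a mean of 10% or less), and the plan does not connect the two

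*Combined protocol and SAP*

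**What the plan says.** The only verdict rule is in the Primary Objective: the protocol counts as ineffective if the "percentage of time the NOL index exceeds the threshold of 25, relative to the observation time, is greater than 25" per cent. That section does not say whether the percentage is a group mean, another group summary or one patient's value.

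Sample Size Determination works with a mean. At most 10% of the observation interval is the null hypothesis, and at least 25% is regarded as indicating a nociceptive stimulus. The calculation is described as "By calculating the sample size for a single mean, setting the type I error α to 0.05", with "power β to 0.8, estimating a standard deviation of 30%, the sample size in the study is determined to be 34 subjects". Sidedness is not stated.

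Statistical Analysis gives tests only for subgroups: for continuous data, "comparisons between subgroups will be performed using Student's t-test for parametric data", with Mann-Whitney as the non-parametric counterpart. It names no one-sample test and no confidence interval for the primary variable. On summaries it says: "Continuous variables will be presented as mean and standard deviation or as median and interquartile range depending on the distribution".

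The NOL cut-off also varies. The Primary Objective uses a strict inequality, and the sizing text opens in the same way ("a nociceptive response measured at NOL >25 is considered" positive), but the two hypotheses are written with NOL ≥ 25.

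**The concern.** The figure 25% has two roles. In the Primary Objective it is a cut-off that the result must exceed. In the sizing it is the assumed true mean at which a test against 10% should succeed. Observing more than 25% and rejecting 10% are different decisions, and the stated power of 0.8 describes only the second.

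Two things are at stake. A reader may take 0.8 as the chance of reaching the protocol's own verdict. And some results would reject the sizing null without meeting the verdict rule; because the plan does not say how to reconcile them, the emphasis could be chosen after the data are seen.

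**Working it through.** **Inputs.** From Sample Size Determination: null mean 10%, alternative 25% (difference 15 points), SD 30 points, alpha 0.05, power 0.8, n = 34. From the Primary Objective: cut-off 25%.

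**1. Reproducing 34.** For a one-sample t-test the noncentrality is (15/30)·√n.
- Two-sided 0.05: power is 0.795 at n = 33 and 0.808 at n = 34, so 34 reproduces.
- One-sided 0.05: power is 0.798 at n = 26 and 0.812 at n = 27, so 27 would have been enough.
- Two-sided normal approximation: (30 × (1.960 + 0.842)/15)² = 31.4, giving 32.

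The two-sided t-test is therefore inferred as the basis of the 34.

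**2. Where the two decisions fall.** SE = 30/√34 = 5.145 and t(0.975, 33) = 2.0345. At an observed SD of 30, the test rejects 10% once the observed mean exceeds 10 + 2.0345 × 5.145 = 20.47%. The Primary Objective needs more than 25%.

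**3. Probability of each decision, if the verdict concerns the observed group mean.** For the rule, P(observed mean > 25) = 1 − Φ((25 − μ)/5.145). For rejecting 10%, the noncentral t applies, with noncentrality (μ − 10)/5.145.

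| True mean μ | Observed mean > 25% | Reject 10% |
|---|---|---|
| 20% | 0.166 | 0.471 |
| 25% | 0.500 | 0.808 |
| 30% | 0.834 | 0.965 |
| 35% | 0.974 | 0.997 |

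The rule reaches 80% at 25 + 0.8416 × 5.145 = 29.3%.

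**4. Results between the two cut-offs.** At a true mean of 25%, P(20.47 < observed mean ≤ 25) = Φ(0) − Φ(−4.53/5.145) = 0.311.

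**5. Sensitivity to the SD and the normal model.** On a 0–100% scale with mean 10%, the SD cannot exceed √(10 × 90) = 30, so smaller SDs were also tried (an assumption). At a true mean of 25%:
- SD 25: power to reject 10% is 0.92; the zone is 18.7–25% and holds 43% of trials.
- SD 20: power is 0.99; the zone is 17.0–25% and holds 49% of trials.
- The rule stays at 0.50 in both. Its 80% point at SD 20 is 25 + 0.8416 × 20/√34 = 27.9%.
- With an assumed beta distribution (SD 30/25/20), the rule is met with probability 0.49 each time, and 10% is rejected with probability 0.87/0.97/1.00.

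**6. Other readings of the verdict.** If it required a two-sided 5% test showing a mean above 25%, the probability at a true mean of 25% would be 0.025. If it used the sample median, the beta model at SD 30 gives about 0.04. If it is per patient, no probability for the group can be computed, because no rule combines patients.

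**The case against.** **The group-mean reading is an inference.** This stands. The Primary Objective names no mean, and Secondary Objectives 3 to 5 correlate the primary objective with pain scores and rescue analgesia, which needs a value for each patient. The probabilities in the table are conditional on the group-mean reading. A per-patient reading does not restore 0.8, however, because 34 was not sized for it.

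**The 50% says little about this design.** It arises at any sample size and any SD when the true mean equals the cut-off, and exactly 25% is the least favourable point of an alternative written as at least 25%. At 30% and 35% the rule does well. This also stands, and it is the reason why 0.8 cannot be read as the chance of the verdict. It does not show that 34 is too few.

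**The sizing may be just what was intended.** The sizing text also gives a mean of at least 25% a clinical meaning, so 25% may be the effect worth detecting and the test against 10% the formal analysis. For that test 0.8 is right. But the plan never names the test as its analysis, and the Primary Objective states a different rule.

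**Stronger inferences that the documents do not support.** A reader might infer that the sample size is wrong; it reproduces. A reader might infer that the plan promises an 80% chance of the ineffective verdict; it never says so. A reader might infer that there is no conclusion at all between 20.5% and 25%; the rule simply withholds the label there, and what is missing is how this fits with rejecting 10%. Nor is there a risk of frequent false verdicts of ineffective: at a true mean of 10% the rule is met with probability of only 0.0018.

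**Conclusion.** The mismatch is real, and confidence in it is high: the stated power belongs to rejecting a mean of 10%, the stated verdict is a comparison with 25%, and no text joins them. None of the readings examined gives the Primary Objective's rule an 80% probability at the planning mean of 25%.

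The size of the effect is held with moderate confidence, because it depends on the group-mean reading. On that reading, with SD 30%, n = 34 and a normal model, the rule has a probability of 0.50 against 0.81 for the sized test at a true mean of 25%, and about 31% of trials reject 10% without meeting the rule. The critical value of 20.5% also assumes a two-sided test, which is inferred from the 34. The consequence is a power claim that can be misread and a conclusion left open in part of the range.

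The missing primary analysis adds to this: a switch to the median would change the quantity that was sized.

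**What to change.** Keep 34 patients and change the wording in three sections.

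1. **Primary Objective.** State that the verdict concerns the mean over patients of each patient's percentage of observation time above the NOL cut-off, or state another unit. Use one sign (> or ≥) throughout. Always report this mean with a 95% confidence interval, whatever the normality test shows, and give the median and interquartile range in addition.
2. **Statistical Analysis.** Name the two-sided one-sample t-test against 10% as the analysis for which the 34 were sized, and limit its conclusion to the mean exceeding 10%.
3. **Decision rule.** State which of 10% or 25% decides that the protocol is ineffective. This is the sponsor's choice. If 25% is kept, report the verdict with the confidence interval relative to 25%, do not infer it from rejecting 10%, and give the wording for a mean that exceeds 10% but is not above 25%.
4. **Sample Size Determination.** Restate the power: about 81% to exclude 10% if the true mean is 25%. Add that, on the group-mean reading, an observed mean above 25% has a probability of about 50%, 83% and 97% at true means of 25%, 30% and 35%.

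This needs no extra patients or data. The cost is a narrower power claim and a position relative to 25% that will often be inconclusive. At SD 30% the interval's half-width is about 2.0345 × 5.145 = 10.5 points, and it includes 25% with probability 0.95 at a true mean of 25%, 0.84 at 20% or 30%, and 0.53 at 35%.

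### Secondary endpoint 2 counts NOL peaks above 40 without dividing by observation time, so it mixes peak frequency with length of surgery

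*Combined protocol and SAP*

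**What the plan says.** Secondary Objectives lists two measures taken directly from the NOL trace. The first is "Time the NOL index exceeds the threshold of 25, expressed in minutes" and the second is "Number of peaks with NOL index above 40". Neither has a denominator.

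The Primary Objective is scaled. The sedation protocol is called ineffective if "the percentage of time the NOL index exceeds the threshold of 25, relative to the observation time, is greater than 25" per cent. The observation period covers "the interval between reaching an adequate sedation level (Bispectral Index - BIS between 40 and 60) and the end of surgical stimulation", so it is specific to each patient.

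On duration, the rationale speaks of "relatively short surgical procedures (lasting between 30 and 90 minutes"), while Study Design says "short-duration (less than 90 minutes") and gives no lower limit.

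The Statistical Analysis section plans descriptive summaries. It then names t, Mann-Whitney, chi-square and Fisher tests under a general clause: "Any sub-analyses and comparisons between subgroups will be performed" with one or other of them. It mentions no rate, offset or adjustment for duration. The surgical procedure performed is among the variables collected.

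**The concern.** A count of events is interpretable across patients only if they are observed for similar lengths of time, or if the count is divided by that time. Here the period can vary three-fold or more, so a high count may reflect frequent peaks or simply a longer operation. The plan recognises this for the primary endpoint, which is a percentage of observation time, but not for the peak count.

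The practical risk lies in comparisons. Different operations tend to have different lengths, and type of procedure is an obvious subgroup factor. If peak counts are compared between procedures with the unadjusted tests on offer, the longer operation can look more nociceptive at an identical hourly rate. In a study asking whether a sedation protocol controls nociception, that could be misread as the protocol failing for one kind of surgery.

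**Working it through.** **The plan's own figure.** Sample Size Determination gives 34 subjects for a single mean of 10% against 25%, SD 30%, alpha 0.05, power 0.8. The normal approximation is (30 × (1.960 + 0.842) / 15)² = 31.4. The exact two-sided one-sample t calculation gives n = 34 with power 0.808, so the figure is reproduced. It rests on the primary percentage only, and nothing below changes it.

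**Dependence on duration.** Take procedure length as a stand-in for observation time.
- Expected peaks = rate × time. At an illustrative 4 per hour: 4 × 0.5 = 2 peaks in 30 minutes and 4 × 1.5 = 6 in 90 minutes.
- Minutes above 25 = fraction × time. At 25% of the time: 0.25 × 30 = 7.5 minutes and 0.25 × 90 = 22.5 minutes.

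Each total triples with no change in intensity.

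**How much of the variation is duration?** For minutes, write M = f × T, with f the fraction of time above 25 and T the observation time, assumed independent. Then Var(M) = E[T]²Var(f) + E[f]²Var(T) + Var(f)Var(T). The plan supplies mean f = 0.25 and SD 0.30. The distribution of T is an assumption.
- T uniform on 30–90: E[T] = 60 and Var(T) = 60²/12 = 300. The terms are 3600 × 0.09 = 324, 0.0625 × 300 = 18.75 and 0.09 × 300 = 27, total 369.75. The shares are 88% fraction, 5% duration, 7% interaction.
- T uniform on 10–90: E[T] = 50 and Var(T) = 80²/12 = 533.3. The terms are 225, 33.3 and 48, total 306.3. The shares are 73%, 11% and 16%.
- With T on 30–90, duration matches the fraction only if the SD of f falls to about 7 points (50% against 47%).

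For peaks the documents give neither a rate nor a variance. With 2–10 per hour assumed and T on 30–90, duration explains 4–7% of the count variance and the patient's own rate 60–83% when the between-patient CV is 1.0–1.2. The two are about equal (12–30% against 13–32%) only at CV 0.3.

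**False-positive rate in a subgroup comparison.** Two groups of 34/2 = 17, with equal true peak rates in both. Assumptions: 3–6 peaks per hour, gamma variation between patients, Poisson counts, Mann-Whitney at nominal 5%.

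| Durations in the two groups (min) | CV 0.5–0.8, raw count | CV 1.2, raw count |
|---|---|---|
| 30–60 vs 60–90 (separated) | 24–53% | 14–15% |
| 30–75 vs 45–90 (overlapping) | about 9–18% | about 7% |
| Same distribution | 4–5% | 4–5% |

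The same test on counts per hour rejects about 5%.

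For minutes above 25 (beta-distributed fraction, mean 25%, SD 30 points), rejection is 9–11% with separated durations, 6% with overlap and 5% with equal durations. With separated durations it rises to 29% at SD 20 and 54% at SD 15. The primary percentage stays at about 5%.

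**The case against.** Three stronger readings are tempting, and the documents do not support them.

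- A reader might infer that these totals measure length of surgery as much as nociception. Under the plan's SD of 30 points, duration accounts for only about 5–11% of the variance of minutes at a mean of 25%. For peaks the documents give nothing from which to establish such a claim. The SD of 30 is itself an estimate made without prior studies; a smaller true SD would raise duration's share.
- A reader might infer that every subgroup comparison is confounded. It is not: when durations match, the error rate is nominal. Confounding needs a factor associated with duration, and the fully separated split is a deliberately clear case rather than an expected one.
- A reader might infer that the plan commits these totals to unadjusted tests. The clause is generic and conditional. It names no subgroup and assigns neither endpoint to a test. The definite plan for them is descriptive, and a raw total is legitimate there.

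It is also fair to say that the measures bearing on the conclusion are already scaled. Objectives 3 to 5, for example "Evaluate any correlation between the primary objective and the NRS scale 15 minutes post-operation", use the primary measure and not the totals. Minutes above 25 divided by observation time is the primary endpoint itself, so keeping it in minutes adds absolute burden and is not a fault.

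This narrows the point to the peak count. That count has no scaled counterpart anywhere in the plan, and the general clause would allow it to be compared without adjustment.

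**Conclusion.** The point holds for secondary endpoint 2, with limited consequences. The peak count combines frequency with an observation period that can vary three-fold or more. If it is compared across a factor linked to duration, the false-positive rate is about 7–18% with partly overlapping durations and 14–53% with fully separated ones, against a nominal 5%. It is nominal when durations match.

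These percentages rest on assumed rates of 3–6 per hour, between-patient CVs of 0.5–1.2, 17 patients per group and uniform durations, none of which the documents give. They show what could happen in such a comparison and do not forecast this study's error rate. The threat is to the interpretation of one secondary endpoint.

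**What to change.** Define secondary endpoint 2 as the number of peaks with NOL above 40 per hour of observation, and report the raw count beside it. For any subgroup comparison, use this rate, or a count model (for example negative binomial) with log observation time as offset.

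Keep minutes above 25 as a descriptive measure of absolute burden, shown with observation time, and use the primary percentage for any comparison.

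Add the start and end of observation to the list under Collection and Management of Clinical Data. They are not named there, but the primary endpoint cannot be computed without the observation time. The cost is a sentence or two in the plan, with no extra measurement on patients and no change to the sample size.

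### Does the lack of a recorded time of first surgical stimulus undermine the percentage of time with NOL above 25?

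*Combined protocol and SAP*

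**What the plan says.** The Primary Objective sets the denominator: "The NOL Index observation time is defined as the interval between reaching an adequate sedation level", meaning BIS between 40 and 60, "and the end of surgical stimulation". The measure is "the percentage of time the NOL index exceeds the threshold of 25, relative to the observation time", and the protocol is called ineffective when it is greater than 25%. The Study Flow-chart agrees on the start: "As soon as the sedation plan shows a Bispectral Index between 40 and 60, the observation of the NOL Index will begin". It then gives the order of events as mask placement, mechanical ventilation and surgery.

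Secondary objectives 1 and 2 are "Time the NOL index exceeds the threshold of 25, expressed in minutes" and "Number of peaks with NOL index above 40". Objectives 3 to 5 relate the primary measure to pain scores at 15 minutes and 2 hours and to rescue analgesia.

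Under Collection and Management of Clinical Data, the clinical items are the procedure performed, heart rate, blood pressure, oxygen saturation, BIS, NOL and NRS. No event times are listed, and the Statistical Analysis section plans no split by phase. The rationale speaks of operations of 30 to 90 minutes, whereas the Study Population covers patients "who need to undergo surgical procedures lasting less than 90 minutes and particularly painful", with no lower limit.

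**The concern.** The window mixes two unlike periods: a pre-surgical one, with an airway manoeuvre and possibly some waiting, and the operation itself. A reader of the result may take time above NOL 25 as the response to surgery. If the pre-surgical period is quiet, it dilutes the surgical share. If mask placement provokes a response, it inflates that share.

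A pre-surgical period of similar length weighs more in a short operation. Short and long procedures could therefore differ in the whole-window percentage while having the same surgical share, and the missing lower limit on duration widens the scope for this. The counts of minutes and peaks carry the same ambiguity if taken over the same window. At stake would be the interpretation of a verdict that turns on a single cut at 25%, with no planned data item that would allow the split later.

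**Working it through.** **The plan's own figure.** Sample Size Determination gives a null mean of 10%, an alternative of 25%, SD 30%, alpha 0.05 and power 0.8. The standardised difference is (25 − 10)/30 = 0.5. A two-sided one-sample t-test (noncentral t) has power 0.795 at n=33 and 0.808 at n=34, so the stated 34 reproduces. Both means refer to the observation interval, so the pre-surgical period is already inside them.

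**How far the two percentages can differ.** Let S be surgical minutes, T pre-surgical minutes, and p the share of T above threshold. The documents give neither T nor p, so both are assumptions. With a surgical share of 25%:

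whole window = (0.25·S + p·T)/(S + T) = 25% + (p − 25%)·T/(S + T)

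The shift is zero when p = 25% and changes sign there. For T of 5, 10 and 15 minutes:

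| S | weight T/(S+T) | whole window, p=0 | whole window, p=50% |
|---|---|---|---|
| 30 min | 14.3 / 25.0 / 33.3% | 21.4 / 18.8 / 16.7% | 28.6 / 31.2 / 33.3% |
| 90 min | 5.3 / 10.0 / 14.3% | 23.7 / 22.5 / 21.4% | 26.3 / 27.5 / 28.6% |

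The gap between 30- and 90-minute operations with equal surgical shares is 2.3, 3.8 or 4.8 points at either extreme of p, with opposite signs, and 0 at p = 25%.

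**Cohort mean.** Assume S is uniform on 30 to 90 minutes. The mean weight is T·ln((90+T)/(30+T))/60.
- T=10: 10·ln(100/40)/60 = 15.3%. With p = 10% or 40%, the shift is 15 × 0.153 = 2.3 points, giving 22.7% or 27.3%.
- T=15: 15·ln(105/45)/60 = 21.2%. With p = 0 or 50%, the shift is 25 × 0.212 = 5.3 points, giving 19.7% or 30.3%. This is the extreme of the assumed range.

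**Scale.** The 95% half-width at n=34 and SD 30 is 2.035 × 30/√34 = 10.5 points.

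**The reverse reading.** If the whole window shows exactly 25%, the surgical share is (25% − w·p)/(1 − w), with w = T/(S+T) and p anywhere from 0 to 100%. For 5 minutes before a 90-minute operation this is 20.8 to 26.4%. For 10 minutes before a 30-minute one it is 0 to 33.3%. These are outer bounds.

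**What the plan asks.** Study Purpose concerns the efficacy of the sedation protocol. Mask placement happens under that protocol, so a response to it belongs in the measure. None of the five secondary objectives requires a split by phase, and no subgroup by duration is named. The contribution described under Approval from the Competent Authority is knowledge of nociception under deep sedation. Surgery there describes which patients are studied; it does not restrict the period observed.

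**The case for a change.** The strongest case for a change is that the shift would be systematic. If pre-surgical and surgical shares differ, a larger sample does not remove the gap, and even the moderate illustration falls on both sides of the 25% cut. The time of first surgical stimulus costs little to note during the case and may be hard to recover afterwards. The anaesthesia record or monitor may hold it, but the plan neither requires nor links it.

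The factual part stands: the surgical share cannot be obtained from the listed data. The inference to a flaw does not. The gap is between two different quantities, and the plan defines and powers for only one of them, so it is not a bias in the planned estimate. The data list is also weak evidence about what will be kept. It is worded as including items, and it omits the window's start and end, which the percentage needs, and rescue doses, which objective 5 needs. A mask-placement time would add even less, since a before-and-after-surgery split would not use it.

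**Conclusion.** No change to the plan follows. The window is defensible for judging a sedation protocol, and its start is the same in the Primary Objective and the Study Flow-chart. The primary percentage, the 34 patients, the power of 0.808 and the verdict on the protocol are the same with or without the extra time. In the illustrations, the whole-window mean differs from a surgical share of 25% by 2.3 points in the moderate case and 5.3 at the extreme. Both rest on assumed pre-surgical minutes and shares and on durations spread evenly over 30 to 90 minutes. The true difference could be zero or of either sign.

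The time of first surgical stimulus and a descriptive surgical-phase percentage would be an optional addition. They would help a reader locate the response but carry no decision limit or test. Reports should describe the result as applying to the whole sedation window.

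Two wording differences are clerical. The cut-off is written as above 25 in the objective and as at least 25 in the sample-size hypotheses, which matters only for readings of exactly 25. The window closes at the end of surgical stimulation in one section and at the end of the procedure in another, and analysts can take the Primary Objective's definition.
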